#### 3.6.3 Day of Gene Transfer (Day 0)

3.6.4 Vascular delivery via intravascular limb infusion for gene therapy (ILI-GT) All subjects participating in this trial will receive an intravascular limb infusion of rAAVrh74.MCK.GALGT2 delivered **Security of the first cohort is the minimum efficacious** dose as established in primate studies. Once safety is established in the low-dose cohort, the second cohort will receive a 2-fold dose escalation.

- Cohort 1 (n=1), Low Dose: 2.5 x 10^13 vg/kg per leg, delivered bilaterally (to total 5.0 x 10^13 vg/kg per subject)
- Cohort 2 (n=1), High Dose: 5x10^13 vg/kg per leg, delivered bilaterally (to total 1.0 x 10^14 vg/kg per subject)

The intravascular limb infusion approach to vascular gene transfer builds upon previously published methods in mice and non-human primates. The modified approach has been previously approved by the FDA

The subjects will be given sedation utilizing NCH anesthesia protocols that minimize the risk of anesthetic reaction in muscular dystrophy. Peripheral vascular access will be obtained with IV and or arterial approaches.

Infusion reactions:

Infusion will be terminated for evidence of an allergic reaction of **grade 2 or greater**, including anaphylaxis, based upon CTCAE v.4 criteria, and reported using these criteria:

Grade 1: Transient flushing or rash, drug fever <38 degrees C (<100.4 degrees F); intervention not indicated

- Grade 2: Rash, flushing, urticaria, dyspnea, drug fever >38°C: Intervention or infusion interruption indicated; responds promptly to symptomatic treatment (e.g., antihistamines, NSAIDS, narcotics); prophylactic medications indicated for ≤24 hrs
- Grade 3: Prolonged (e.g., not rapidly responsive to symptomatic medication and/or brief interruption of infusion); recurrence of symptoms following initial improvement; hospitalization indicated for clinical sequelae (e.g., renal impairment, pulmonary infiltrates)
- Grade 4: Life-threatening consequences; urgent intervention indicated
- Grade 5: Death

Under CTCAE v.4 criteria, anaphylaxis is by definition grade 3 (Symptomatic bronchospasm with or without urticaria; allergy-related edema/angioedema, hypotension), and would result in infusion termination and systemic treatment.

## 3.7 Post Gene Transfer Monitoring Plan

#### 3.7.1 Up to 48-Hour Inpatient Monitoring (Days 1 and 2)

Patients will be closely monitored for blood vessel rupture, compartment syndrome, and neuromuscular integrity, including by Doppler ultrasound (as needed). Neuromuscular integrity will be assessed by routine assessment of clinical pain and strength.

The subject will see the principal investigator or designee on the morning of **Day 1** for a physical examination as well as review and documentation of concomitant medications and all adverse events/serious adverse events following injection. Vitals including blood pressure, heart rate, respiratory rate, and temperature will be performed as well as the following lab values:

- Complete blood cell count (CBC) and differential, platelet
- Aspartate aminotransferase (AST)/alanine transaminase (ALT)
- Gamma-glutamyl transpeptidase (GGT)\*
- A Comprehensive Metabolic Panel (CMP) that includes:
  - o Albumin/Serum total protein
  - o Serum total bilirubin
  - Electrolytes
  - o Calcium
  - o Creatinine/Blood Urea Nitrogen (BUN)
  - Serum glucose
  - o Alkaline phosphatase
- Creatine kinase (CK)Urinalysis

\* For subjects taking drugs that potentially induce GGT synthesis through the cytochrome P450 system, the clinically significant range will be estimated at two times the levels obtained from the baseline screening test.

A photograph will be taken of each injection site.

On the second day after gene transfer (**Day 2**) the subject will be discharged from the hospital after a physical examination by the principal investigator or designee, as well as review and documentation of concomitant medications, medical history and all adverse events/serious adverse events following injection.

#### 3.7.1.1 Post-injection immune suppression

All subjects will be discharged from the hospital on oral prednisone or prednisolone at 1 mg/kg/day, which will be adjusted according to IFN-gamma T-cell studies in the following weeks.

If the **30 day** post-infusion IFN-gamma T-cell response shows  $\leq$ 50 SFC per 1 x 10^6 PBMCs, the subject's prednisone or prednisolone dose will be decreased back to the standard clinical dose of 0.75 mg/kg/day. Those subjects who had been on deflazacort may be switched to the standard clinical dose of 0.9 mg/kg day. For either regimen, approximations of these target doses may be allowed to account for pill formulations (for prednisone and deflazacort), as in clinical practice. If either the AST and ALT exceeds >2.5X the subject's baseline values, and results are confirmed on a follow-up blood test, the prednisone or prednisolone regimen will be maintained at 1 mg/kg/day until the enzyme levels fall within a range , 2.5X the baseline value.

If the IFN-gamma T-cell response shows  $\geq$ 50 SFC per 1 x 10^6 PBMCs, we may increase the dose to approximately 2 mg/kg/day depending on T-cell response measured by ELISpot assay, and prolong a subsequent tapering protocol based on the individual subject's immune response profile as assessed by subsequent ELISpot assays (as on the schedule discussed below). Based upon other gene transfer trials performed at NCH, we anticipate that oral prednisone or prednisolone may be administered for up to 120 days post gene transfer prior to return to the standard clinical corticosteroid regimen of each subject.

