#### 2.1 Abstract

The proposed clinical trial is a dose escalation study of rAAVrh74.MCK.GALGT2 for DMD patients. There will be a modified intravascular limb infusion(ILI);

 henceforth designated as intravascular limb infusion for gene therapy (ILI-GT) delivered sequentially to the whole each lower limb of DMD subjects via a major lower limb artery.

ILI-GT will be delivered to the muscles of both legs of DMD subjects. This approach to vascular gene transfer builds upon previously published methods used in mice and non-human primates.

Two cohorts will undergo gene transfer in a standard dose escalation scheme to establish maximum tolerated dose (MTD) using toxicity. One subject will be enrolled into the first cohort and one subject will be enrolled in the second cohort. The first cohort will receive the minimally efficacious dose as established by primate studies, consisting of  $2.5 \times 10^{13}$  vg/kg per leg, delivered bilaterally (to total  $5.0 \times 10^{13}$  vg/kg per subject). Once safety is established in the low-dose cohort, the second cohort will receive  $5 \times 10^{13}$  vg/kg per leg, delivered bilaterally (to total  $1.0 \times 10^{14}$  vg/kg per subject).

The baseline open muscle biopsy will be performed in one quadriceps muscle. Open muscle biopsy of the quadriceps (in the leg contralateral to the pre-treatment biopsy) will be performed at 90 days post ILI-GT procedure.

Every effort

will be made to sample these same muscles in all patients; however, in subjects (particularly older ambulant subjects) with limited quadriceps musculature, alternate muscle biopsy sites may be selected at the PIs discretion (including gastrocnemius or tibialis anterior muscles).

The primary objective of this study is the assessment of the safety of intravascular administration of rAAVrh74.MCK.GALGT2 to DMD patients. Safety endpoints will be assessed by changes in hematology, serum chemistry, urinalysis, immunologic response to

rAAVrh74 and GALGT2, and reported history and observations of symptoms. Efficacy measures will be used as secondary outcome for this disorder including a combination of functional 6 minute walk test (6MWT) and direct muscle testing for strength (MVICT) of lower limb muscles.

Subjects will be evaluated at baseline, infusion visit (days 0-2), and return for follow up visits on days 7, 14, 30, 60, 90, and 180 and months 12, 18 and 24.

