The baseline evaluation will take place over two visits (one to two weeks apart). Because a preexisting antibody response would be exclusionary, ELISA and ELISpot testing will be performed at the first visit, allowing the results to be reviewed prior to the muscle biopsy with its attendant risks (including sedation). Prescribed and over the counter medications used in the prior two weeks will be recorded at the baseline visit and changes in these medications will be recorded during each subsequent visit. The PI will encourage participants to maintain the medication and supplements they are on at enrollment through the course of the study.

Subjects must already be on prednisone, prednisolone, or deflazacort for at least 12 weeks at time of enrollment as part of the inclusion criteria.

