#### 3.6.2 Pre Infusion Visit (Day -1)

Subjects will arrive to the Nationwide Children's Hospital within 24 hours prior to gene transfer. They will undergo a physical exam, a review of concomitant medications and updates to the medical history. Vital signs (heart rate, respiratory rate, temperature, and blood pressure) and weight will be obtained.

- The labs obtained on Day -1 will include:
- Complete blood cell count (CBC) and differential, platelets
- Aspartate aminotransferase (AST)/alanine transaminase (ALT)
- Gamma-glutamyl transpeptidase (GGT)\*
- Prothrombin time (PT)/activated partial thromboplastin time (PTT)
- Creatine kinase (CK)

\* For subjects taking drugs that potentially induce GGT synthesis through the cytochrome P450 system, the clinically significant range will be estimated at two times the levels obtained from the baseline screening test.

An ELISpot for T-cell responses to AAVrh74 and GALGT2 will also be performed.

In previous gene therapy studies at NCH, there has been observed an antigen specific T-cell response to the AAV vectors. This is an expected response between 2 - 4 weeks following gene transfer. One possible consequence to such antigen specific T-cell responses is clearance of the transduced cells and loss of transgene expression. All subjects will already be on prednisone, prednisolone, or deflazacort for 12 weeks at time of enrollment as part of the inclusion criteria. The standard clinical dose of prednisone or prednisolone is 0.75 mg/kg/day, and the standard clinical dose of deflazacort is 0.9 mg/kg/day. In order to dampen the host immune response to our AAV-based therapy, for each subject the glucocorticoid dose will be increased to prednisone or prednisolone 1.0 mg/kg/day, not to exceed 60 mg/day; subjects on deflazacort at enrollment will be placed on prednisone or prednisolone for the immediate peri-injection period. This prednisone dose will be delivered beginning one day prior to the gene transfer and only after passing all inclusion and exclusion criteria (in the event that a measure is repeated on Day -1). This corticosteroid regiment will be continued after gene transfer as discussed in Section 3.7.1, followed by a return to the pre-treatment corticosteroid regimen.

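### The ELISpot steroid rule in section 3.7.1.1 puts a result of exactly 50 SFC in both its decrease and its increase branch, and the increase branch names no visit

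*Combined protocol and SAP*

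**What the plan says.** Under section 3.7.1.1, subjects leave hospital on prednisone or prednisolone at 1 mg/kg/day, and the dose is then adjusted over the following weeks by IFN-gamma T-cell results. Two sentences set the thresholds:

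- **Lower branch.** It is tied to the Day 30 result and applies at 50 SFC per million PBMCs or fewer: "the subject's prednisone or prednisolone dose will be decreased back to the standard clinical dose of 0.75 mg/kg/day".
- **Upper branch.** It applies at 50 SFC per million PBMCs or more, with no visit named: "we may increase the dose to approximately 2 mg/kg/day depending on T-cell response measured by ELISpot assay". The later taper may then be prolonged, "based on the individual subject's immune response profile as assessed by subsequent ELISpot assays".

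The same section has a liver-enzyme rule that compares AST and ALT with 2.5 times the subject's own baseline.

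ELISpots are also taken before transfer: at screening (section 3.6.1; Visit 1 in Table 2) and on Day -1, where section 3.6.2 states: "An ELISpot for T-cell responses to AAVrh74 and GALGT2 will also be performed". Section 3.7.1.1 mentions neither. The immune exclusions in section 3.2 are two antibody criteria (AAVrh74 binding antibody and anti-Sda); there is no T-cell limit. For the primary safety objective, section 2.1 says: "Safety endpoints will be assessed by changes in hematology, serum chemistry, urinalysis, immunologic response to" the vector and GALGT2.

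**The concern.** A threshold rule should send every possible result to one branch. This one sends 50 SFC to two, and they move the dose in opposite directions from the 1 mg/kg/day in place. A site holding a Day 30 result of 50 could follow either sentence and be compliant.

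The missing visit adds a second uncertainty. A reader cannot tell whether the upper branch is the other half of the Day 30 decision or a standing rule for any ELISpot after transfer.

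The rule governs steroid exposure for a period that section 3.7.1.1 expects to last up to 120 days. The protocol itself says steroids raise neutrophil and leukocyte counts (section 4.5) and increase strength (section 2.3.3). Laboratory safety is part of the primary outcome, and strength is tested at Day 90, inside that period. With one subject per dose, no other subject at that dose would show how the rule was applied.

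The silence on the pre-transfer ELISpots is a smaller matter. A subject with a T-cell response before transfer is eligible and could meet the upper condition with no change at all. The text does not say whether that is intended.

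**Working it through.** The plan gives no figure to reproduce for this rule, so the check is one of logic, with a little arithmetic for size.

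**1. The branches at and around the threshold (Day 30 result, SFC per million PBMCs).**

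| Result | Lower branch (≤50, dose will be reduced) | Upper branch (≥50, dose may be increased) |
|---|---|---|
| 45 | applies | – |
| 49 | applies | – |
| 50 | applies | applies |
| 51 | – | applies |
| 55 | – | applies |

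The overlap is the single value 50. If either inequality were strict, it would vanish.

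**2. Distance between the two actions.** The doses in section 3.7.1.1 are 1 mg/kg/day (in place), 0.75 mg/kg/day (lower branch) and about 2 mg/kg/day (upper branch).

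- Lower branch: 0.75/1 = 0.75, a fall of 25%.
- Upper branch, taken in full: 2/1 = 2, a doubling.
- Ratio of the two end points: 2/0.75 = 2.67.

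**3. Can a result of exactly 50 occur?** The documents do not give the number of cells read, so I assume a range of N = 0.2, 0.6 and 1.0 million. One spot is then 1/N SFC per million, and 50 SFC corresponds to k = 50N = 10, 30 or 50 spots. All are whole numbers, so 50 is attainable across that range. If spot counts are Poisson with mean m = (true level) × N (also an assumption), the chance of reading exactly 50 is e^(−m) m^k / k!:

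| True level | N = 0.2 million | N = 0.6 million | N = 1.0 million |
|---|---|---|---|
| 40 | 0.099 | 0.036 | 0.018 |
| 50 | 0.125 | 0.073 | 0.056 |
| 60 | 0.105 | 0.043 | 0.023 |
| 100 | 0.006 | <0.001 | <0.001 |

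Even when the true level is exactly 50, the overlap is hit in about 6% to 13% of readings; well away from 50 it is rare.

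**4. What the missing visit changes.** Table 2 schedules post-transfer ELISpots on Days 7, 14, 30, 60, 90 and 180 and at Months 12, 18 and 24. Five of these (Days 7, 14, 30, 60 and 90) fall within 120 days. If the upper branch refers back to the Day 30 result named just before it, it covers one of the five. If it takes its scope from the section's opening sentence, it can cover all five. The lower branch names Day 30 alone, so on either reading the overlap at 50 arises only there.

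**5. The pre-transfer value.** Take a subject at 60 SFC on Day -1 and 60 SFC after transfer. The change is 60 − 60 = 0, yet 60 ≥ 50, so the upper condition is met. The AST/ALT rule in the same section would not behave this way, because it is scaled to the subject's baseline.

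**The case against.** The strongest reply is that the two sentences are not equal commands. The lower branch is mandatory; the upper is permissive and depends on the T-cell response. At 50 there is one instruction and one option, so an investigator who reduces the dose breaks no rule. The conflict also touches one value in a two-subject trial. This stands, and it limits the size of the point. It does not remove it: a mandatory decrease and a permitted increase cannot both be open for the same result.

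A second reply concerns baseline. Section 3.6.2 gives the purpose of the added steroid as dampening an immune response that could clear transduced cells. That aim does not obviously depend on when the T cells arose, so an absolute threshold may be a deliberate clinical judgement. This also stands. The documents do not show the absolute threshold to be an error, only that they are silent on the earlier samples.

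Some stronger conclusions are tempting, but the documents do not support them:

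- *A pre-existing response would be reported as a vector effect.* Section 2.1 assesses changes in immunologic response, and section 3.12 sends all data to the DSMB as gathered, which includes the pre-transfer ELISpots. The board could see a 60-to-60 pattern.
- *It would drive escalation.* Sections 3.5 and 4.6 base escalation on dose-limiting toxicity, which section 4.2 ties to unanticipated, related events of Grade 3 or higher. Section 4.6 also mentions a wider safety and efficacy analysis but sets no ELISpot criterion.
- *The increase branch is triggered from Day 7.* That is one reading of a sentence that names no day.
- *Section 3.6.1 implies a T-cell exclusion.* It explains first-visit ELISA and ELISpot testing by an exclusionary antibody response. Pairing the assays is loose wording; eligibility under section 3.2 is unaffected.

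**Conclusion.** The overlap is an error as written: at exactly 50 SFC per million PBMCs, section 3.7.1.1 both requires a decrease and permits an increase. It rests only on the two inequality signs as they stand in that section. It is small in reach (one value, at Day 30, for at most two subjects). The 2.67-fold gap between end points is an upper figure that assumes the optional increase is taken in full. The 6% to 13% chance of meeting the overlap applies only when the true level is 50, and it depends on the assumed cell numbers and Poisson counts.

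The unnamed visit in the upper branch is a genuine ambiguity in the same sentence and should be settled with it.

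The absence of the pre-transfer ELISpot from the rule is a secondary note. It calls for a statement of intent and a clearer display of data already collected. No sample size, error rate or escalation criterion is affected.

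**What to change.** 1. Reconcile the two threshold sentences in section 3.7.1.1 so that exactly one branch contains 50 SFC per million PBMCs. Which branch that is, and the dosing attached to it, is for the sponsor to decide.
2. In the same sentences, state which visit or visits the upper branch applies to.
3. State in section 3.7.1.1 whether a response already present at screening or on Day -1 enters the rule, and if so how. A sentence confirming that the threshold is meant to be absolute would be enough, if that is the intention.
4. Add to the DSMB report contents in section 6.3.2 that the Day 30 report shows the AAVrh74 and GALGT2 ELISpots beside their Day -1 values. This makes the report consistent with the wording on changes in section 2.1.

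The cost is a short protocol amendment and one added listing. The screening and Day -1 samples are already scheduled, so no new sampling or assay is needed.

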#### 3.7.2 Post-Gene Transfer Monitoring (Days 7, 14, 30)

Subjects will return for follow up visits on **Days 7, 14, and 30** after treatment, with repeat physical examination, review of concomitant medications, updates to the medical history, adverse events, vital signs (heart rate, respiratory rate, temperature, weight, and blood pressure) and blood and urine studies at each visit.

Lab work will include the following:

- Complete blood cell count (CBC) and differential, platelets
- Aspartate aminotransferase (AST)/alanine transaminase (ALT)
- Gamma-glutamyl transpeptidase (GGT)\*
- A Comprehensive Metabolic Panel (CMP) that includes:
  - Albumin/Serum total protein
  - Serum total bilirubin
  - o Electrolytes
  - o Calcium
  - Creatinine/Blood Urea Nitrogen (BUN)
  - Serum glucose
  - Alkaline phosphatase

- Prothrombin time (PT)/activated partial thromboplastin time (PTT)
- Amylase
- Urinalysis
- •
- ELISpots for T-cell responses to AAVrh74 and GALGT2
- Creatine kinase (CK)#

•

\* For subjects taking drugs that potentially induce GGT synthesis through the cytochrome P450 system, the clinically significant range will be estimated at two times the levels obtained from the baseline screening test. # CK will not occur on Day 14

On **Day 30**, additional tests will include an ELISA for detection of total antibodies to AAVrh74, Cystatin C, and whole blood banking to investigate vector shedding.

To facilitate these scheduled visits, all subjects will remain in the Columbus metropolitan area for a minimum of two weeks following gene transfer. If there is a systemic immune response that leads to acute respiratory distress syndrome, which implies a severe inflammation of the lung parenchyma, the patient would be hospitalized and treated aggressively with fluid replacement for hypotension if necessary and receive pulse methylprednisolone treatment (1 gram per day) over 3-5 days.

# 3.7.3 Post-Gene Transfer Monitoring after Day 30 (Days 45, 60, 75, 90, 180; Months 12, 18, and 24)

After the follow-up visit at Day 30 post treatment, subjects will continue outpatient active monitoring through 2 years post-gene transfer. Subjects will return for follow-up visits at Days 60, 90, and 180 and at Months 12, 18 and 24 after treatment. Please refer to the graphical Study Timeline of Events below for a summary of studies and procedures at each visit.

At Days 45 and 75, targeted safety labs will be drawn, assessing liver function (AST, ALT, and GGT). For convenience, for subjects outside of the Columbus area, these may be locally drawn and shipped to the NCH clinical laboratory.

The **Day 60 visit** safety assessments include updates to the medical history, physical examination, concomitant medications, vital signs (heart rate, respiratory rate, temperature, weight, and blood pressure) and blood work, including: AST, ALT, GGT, ELISA for detection of serum total antibodies to AAVrh74 and ELISpots for T-cell responses to AAVrh74 and GALGT2. Urine and whole blood will be banked for possible vector shedding studies.

The Day 90, Day 180, 12 month, 18 month, and 24 month visits include updates to the medical history, physical examination, concomitant medications, vital signs (heart rate, respiratory rate, temperature, weight, and blood pressure, height), ECG, echocardiogram, and the following blood and urine studies:

- Complete blood cell count (CBC) and differential, platelets.
- Aspartate aminotransferase (AST)/alanine transaminase (ALT)
- Gamma-glutamyl transpeptidase (GGT)\*
- A Comprehensive Metabolic Panel (CMP) that includes:
  - Albumin/Serum total protein
  - Serum total bilirubin
  - $\circ$  Electrolytes

- o Calcium
- Creatinine/Blood Urea Nitrogen (BUN)
- o Serum glucose
- Alkaline phosphatase
- Prothrombin time (PT)/activated partial thromboplastin time (PTT)
- Creatine kinase (CK)
- Cystatin C
- Urinalysis
- ELISpots for T-cell responses to AAVrh74 and GALGT2
- ELISAs for detection of serum total antibodies to AAVrh74

\* For subjects taking drugs that potentially induce GGT synthesis through the cytochrome P450 system, the clinically significant range will be estimated at two times the levels obtained from the baseline screening test.

At each of these time points, functional testing will be performed, including the video-recorded 6 MWT, the 100 m walk/run, the NSAA, and MVICT. In addition, at the **Day 180, 12 month**, **18 month**, and **24 month visits**,

